**Table C Liver Function Markedly Abnormal Criteria**

Liver Function Parameter	Criteria
ALT	$\geq 3 \times \text{ULN}$
	$\geq 5 \times \text{ULN}$
AST	$\geq 3 \times \text{ULN}$
	$\geq 5 \times \text{ULN}$
Total Bilirubin (in combination with ALT or AST criteria)	$> 1.5 \times \text{ULN}$
	$> 2 \times \text{ULN}$
Hy's Law Components	Criteria
ALT or AST	$\geq 3 \times \text{ULN}$
Total Bilirubin	$> 2 \times \text{ULN}$
Alkaline phosphatase	$< 2 \times \text{ULN}$

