17. Has a presence or history of clinically significant liver disease, including active viral hepatitis or cirrhosis. Participants with a prior history of liver disease which is now inactive or successfully treated may be eligible if liver function values (ie, aspartate aminotransferase [AST], alanine aminotransferase [ALT], total bilirubin) have been normal for the past year and are within the normal range (per central laboratory) at V1. Liver function testing may be repeated once prior to V2 at the discretion of the Investigator if results are inconsistent with the participant's clinical status or recent laboratory results.

18. Has a history of malabsorptive surgical procedures (eg, Roux-en-Y gastric bypass, jeunoileal bypass, biliopancreatic diversion).

Other Medical Disorders:

19. Has a history of malignancy \leq 5 years before signing the informed consent except for adequately treated basal cell or squamous cell skin cancer.

Note: Participants with a history or presence of liver tumors (benign or malignant) or sex steroid-influenced malignancies (eg, genital organs, breasts) are excluded regardless of the interval since the history of the malignancy.

20. Has a history or presence of meningioma.

21. Has any disease that may worsen under hormonal treatment such as disturbances in the bile flow (presence of or history of cholestasis, presence of gallstones), systemic lupus erythematosus, pemphigoid gestationis or idiopathic icterus during a previous pregnancy, middle-ear deafness (otosclerosis), Sydenham chorea, or porphyria.

Note: History of cholecystectomy does not exclude a participant.

22. Has a current or previous history of medically diagnosed severe depression unless the potential participant is determined to be clinically stable and asymptomatic.

23. Has a known allergy/sensitivity or contraindication to NOMAC-E2.
24. Has a history (current or within the past 2 years) of drug or alcohol abuse or dependence.
25. Has any clinically relevant abnormal laboratory result at Screening (V1) as judged by the Investigator.
26. Has a history or current evidence of any condition, therapy, or other circumstance that in the opinion of the Investigator might confound the results of the study, affect participant's well-being, or interfere with the participant's participation for the full duration of the study (ie, approximately 1 year).

Prior/Concomitant Therapy

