8.4.5 Events of Clinical Interest

Selected nonserious AEs and SAEs are also known as ECIs and must be reported to the Sponsor.

Events of clinical interests for this study that require regulatory reporting **within 24 hours** of learning of the event include:

- An elevated AST or ALT lab value that is greater than or equal to $3 \times$ the upper limit of normal (ULN) and an elevated total bilirubin lab value that is greater than or equal to $2 \times$ ULN and, at the same time, an alkaline phosphatase lab value that is less than $2 \times$ ULN, as determined by way of protocol-specified laboratory testing or unscheduled laboratory testing.*

***Note:** These criteria are based upon available regulatory guidance documents. The purpose of the criteria is to specify a threshold of abnormal hepatic tests that may require an additional evaluation for an underlying etiology. The study site guidance for assessment and follow-up of these criteria can be found in the Investigator Study File Binder (or equivalent).

- ATE (including myocardial infarction, stroke, or peripheral arterial events) and VTE (including pulmonary embolism and deep venous thrombosis).

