Appendix 3 Clinical Laboratory Tests

The tests detailed in [Table 12](#) will be performed by the central laboratory, with the exception of STI panel testing, which will be performed by a local laboratory. Otherwise, local laboratory results are only required in the event that the central laboratory results are not available in time for either starting study treatment administration and/or response evaluation. If a local sample is required, it is important that the sample for central analysis is obtained at the same time. Additionally, if the local laboratory results are used to make either a study treatment decision or response evaluation, the results must be entered into the eCRF.

Protocol-specific requirements for inclusion or exclusion of participants are detailed in [Section 5.0](#) of the protocol.

Additional tests may be performed at any time during the study as determined necessary by the Investigator or required by local regulations.

All study-required laboratory assessments will be performed by a central laboratory, with the exception of STI panel testing which will be performed by a local laboratory, and of urine pregnancy tests which will be performed on-site or at the participant's home.

Investigators must document their review of each laboratory safety report.

Table 12 Protocol-required Safety Laboratory Assessments

Hematology	Chemistry	Urinalysis	Other
Hematocrit Hemoglobin Platelet count WBC (total and differential)	Albumin Alkaline phosphatase Alanine aminotransferase Aspartate aminotransferase Bicarbonate Calcium Chloride Creatinine (for determination of eGFR) Glucose (nonfasting) Phosphorus Potassium Sodium Total bilirubin (and direct bilirubin, if total bilirubin is elevated above the ULN) Total protein Blood urea nitrogen	Blood Glucose Protein Specific gravity pH Leukocyte esterase Nitrate Microscopic examination if abnormal results noted on urinalysis	Cervical cytology Serum β -hCG STI panel (local laboratory)

Abbreviations: β -hCG=beta human chorionic gonadotropin; eGFR=estimated glomerular filtration rate; ULN=upper limit of normal; WBC=white blood cell.

Appendix 4 Adverse Events: Definitions and Procedures for Recording, Evaluating, Follow-up, and Reporting

Definition of AE

AE Definition

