**Table A Study Objectives and Endpoints**

Objectives	Endpoints
Primary	
To assess the safety and tolerability of the NOMAC-E2 COC	

• Proportion of participants who had an adverse event

• Abnormalities in clinical laboratory assessments, vital signs, and physical examination

• Proportion of participants who prematurely discontinued study treatment due to adverse events

Abbreviations: COC=combined oral contraceptive; NOMAC-E2=Nomegestrol Acetate + 17 $\beta$ -estradiol

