### **15.3. LABORATORY EVALUATIONS**

Results from the central laboratory will be included in the reporting of this study for hematology, biochemistry, and urinalysis. A list of laboratory assessments to be included in the outputs is included in Appendix 3 of the protocol (Table 10). For each parameter, normal reference ranges and safety ranges will be presented.

Presentations will use International System of Units (SI). Results will be converted as needed prior to the analysis. Quantitative laboratory measurements reported as '< X', i.e., below the lower limit of quantification (LLQ), or '> X', i.e., above the upper limit of quantification (ULQ), will be converted to X for the purpose of quantitative summaries, but will be presented as recorded, i.e., as '< X' or '> X' in the listings.

Document:

Version Number:

2.0

Version Date:

23APR2024

Template No.: CS\_TP\_BS016 Revision 6

Reference: CS\_WI\_BS005

Effective Date: 02Dec2019

Copyright © 2009, 2010, 2012, 2016, 2018, 2019 [REDACTED]. All rights reserved. The contents of this document are confidential and proprietary to [REDACTED]. Unauthorized use, disclosure or reproduction is strictly prohibited.

Actual and change from baseline in laboratory test values will be summarized by visit (including Baseline and last measurement) under each of hematology, biochemistry, and urinalysis. All available lab data will be included in the data listings.

In addition, markedly abnormal liver function-related laboratory tests will be summarized during all visits in the study based on the criteria listed below in Table C.

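### SAP Table C has no raised-ALP and no stand-alone bilirubin criterion, so a cholestatic abnormality with ALT and AST both below 3 × ULN is not counted as markedly abnormal

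*SAP*

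**What the plan says.** SAP section 15.3 states that "markedly abnormal liver function-related laboratory tests will be summarized during all visits in the study based on the criteria listed below in Table C". The first block of Table C, headed "Liver Function Parameter", sets cut-offs for ALT and for AST at ≥ 3 and ≥ 5 × ULN, with no further condition. Its remaining entry is "Total Bilirubin (in combination with ALT or AST criteria"), at > 1.5 and > 2 × ULN. The second block defines Hy's Law: ALT or AST ≥ 3 × ULN, total bilirubin > 2 × ULN, and "Alkaline phosphatase" < 2 × ULN. ALP appears nowhere else in the table.

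SAP Table A lists "Abnormalities in clinical laboratory assessments, vital signs, and physical examination" under the primary safety objective. The protocol synopsis (Primary Safety Analyses) expresses this as a proportion of participants. Protocol 9.4.3.2 promises the incidence of markedly abnormal post-baseline values and leaves the categories to the SAP.

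The data exist. Protocol Table 12 includes ALP in the chemistry panel, as well as "Total bilirubin (and direct bilirubin, if total bilirubin is elevated above the ULN"). Exclusion criterion 21 bars women with "any disease that may worsen under hormonal treatment such as disturbances in the bile flow". The hepatic event of clinical interest in protocol 8.4.5 requires raised ALT or AST and raised bilirubin together with ALP below 2 × ULN.

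**The concern.** A proportion with abnormalities needs a threshold that says who is abnormal. For a raised ALP, or for a raised bilirubin without raised transaminases, the SAP text supplies none. A cholestatic pattern typically shows as a rise in ALP, bilirubin or both, so Table C can miss it whenever the transaminases stay under the cut-off.

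The study is reported synoptically with a focus on safety (SAP section 1). Followed as written, that report could say that no liver test was markedly abnormal while a participant had ALP several times the upper limit and a clearly raised bilirubin. The hepatic event of clinical interest would not fill the gap, because it needs both a raised transaminase and a low ALP.

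**Working it through.** The plan gives no figure to reproduce, and no power or sample-size arithmetic applies. The check is to apply Table C as a rule set to hypothetical results.

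**Inputs (SAP Table C, all in multiples of ULN)**
- ALT row: ALT ≥ 3; ALT ≥ 5.
- AST row: AST ≥ 3; AST ≥ 5.
- Bilirubin row: bilirubin > 1.5; bilirubin > 2; each only if ALT ≥ 3 or AST ≥ 3. This is how I read the words about combination.
- Hy's Law: (ALT ≥ 3 or AST ≥ 3) and bilirubin > 2 and ALP < 2.

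**Step 1: single profiles**

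| ALT | AST | Bilirubin | ALP | Table C criteria met |
|---|---|---|---|---|
| 1 | 1 | 4 | 1 | none |
| 1 | 1 | 1 | 5 | none |
| 2.9 | 2.9 | 4 | 5 | none |
| 3 | 1 | 4 | 5 | ALT ≥ 3; bilirubin > 1.5 and > 2 in combination; not Hy's Law |
| 3 | 1 | 1 | 5 | ALT ≥ 3 |
| 3 | 1 | 3 | 1 | ALT ≥ 3; bilirubin > 1.5 and > 2 in combination; Hy's Law |

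**Step 2: a grid.** ALT and AST each took the values 1, 2.9, 3 and 5; bilirubin 1, 1.6, 2.0, 2.1 and 4; ALP 1, 1.9, 2 and 5. The profiles with ALP ≥ 2 and bilirubin > 2 number 4 × 4 × 2 × 2 = 64.
- ALT and AST both below 3: 2 × 2 × 2 × 2 = 16 profiles, of which 0 are counted.
- ALT or AST ≥ 3: 64 − 16 = 48 profiles, of which 48 are counted in the ALT or AST rows and in the bilirubin rows.
- Hy's Law: 0 of 64, because ALP is ≥ 2 in all of them.

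These fractions describe the chosen grid. They are not incidences.

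**Step 3: does ALP ever add a count?** Raising ALP from 1 to 5 added a criterion in no profile of the grid. This follows from the rules, since ALP enters only as an upper limit within Hy's Law.

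**Step 4: the other reporting routes**
- Descriptive tables (SAP sections 8 and 15.3) give mean, standard deviation, median, minimum and maximum. The maximum shows one extreme value. It does not show how many women crossed a limit, or whether ALP and bilirubin rose in the same woman.
- Listings contain every laboratory value but no count.
- Adverse events (protocol 8.3.4) depend on the investigator's judgement of clinical relevance and feed a separate endpoint in SAP Table A.
- Routine chemistry is scheduled only at V1 and at V7 or early termination (protocol Table 3), so usually a single post-baseline sample carries the information.

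**The case against.** The strongest defence is that the result is still reported. An extreme ALP or bilirubin shows as the maximum at a summarised visit and appears in the listings. SAP 15.3 also says that reference and safety ranges will be shown for each parameter. A result judged clinically significant becomes an adverse event and so reaches another primary safety endpoint. Table C resembles the protocol's own hepatic event of clinical interest, and the protocol left the categories to the SAP. The SAP is a reduced, descriptive plan for a study that stopped early, and its modification history shows that the choice of laboratory outputs was considered. No passage demands a cholestatic category.

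Most of this stands, and it limits the point to a reporting improvement. It does not remove the point, because none of these routes gives a count against a threshold. The ranges come with no stated tabulation of women outside them.

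Three stronger readings are tempting and are not supported:
- **That cholestatic abnormality is never counted, or that Table C sees only hepatocellular injury.** The ALT and AST rows carry no ALP condition. With ALT or AST ≥ 3 × ULN a woman with high ALP is counted there, and in the bilirubin rows if her bilirubin qualifies. High ALP removes her only from Hy's Law.
- **That such values affect nothing but mean change.** The maximum, the listings and the adverse event route remain.
- **That the protocol designates cholestasis as an event to be tracked.** Exclusion criterion 21 concerns existing or past disease and keeps those women out. It supports the relevance of bile flow to hormonal treatment and no more.

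**Conclusion.** The point holds in a limited form. With ALT and AST both below 3 × ULN, Table C counts no ALP or bilirubin abnormality of any size, and the SAP text offers no other abnormality count for a primary safety endpoint that the protocol treats as a proportion.

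Its size in women cannot be given. A reader might apply an assumed incidence to the 1,878 planned participants, but the documents contain no incidence and the study ended early, so the result would be neither an estimate nor a bound.

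The conclusion rests on two assumptions. First, the combination in the bilirubin row means ALT or AST ≥ 3 × ULN; requiring ≥ 5 × ULN would count fewer cases still. Second, the output templates mentioned in SAP section 8, which are not in the text available to me, add no further liver criterion. The change is worth making because it is cheap. The gap does not undermine the rest of the safety analysis.

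**What to change.** Add two reporting rows to Table C and to the accompanying listing, and leave the existing rows unchanged:
1. ALP ≥ 2 × ULN.
2. Total bilirubin > 2 × ULN irrespective of ALT and AST, showing direct bilirubin and the baseline value.

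Add a flag when both occur on the same sample. A third counting row is unnecessary, since every such case is already in rows 1 and 2.

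The multiples are those Table C already uses for ALP and bilirubin. If the sponsor prefers others, the SAP should state them with a reason. Applied to the three uncounted profiles above, isolated bilirubin 4 × enters row 2, isolated ALP 5 × enters row 1, and ALP 5 × with bilirubin 4 × enters both rows and is flagged.

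The cost is SAP wording and a little programming on data already collected. A few benign isolated bilirubin rises will be counted; the direct bilirubin and baseline values help the reader recognise them. The rows govern reporting only and change no clinical rule.

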## 15.4. VITAL SIGNS AND BODY WEIGHT

The following vital signs measurements will be listed:

- Systolic Blood Pressure (mmHg)
- Diastolic Blood Pressure (mmHg)
- Pulse Rate (bpm)
- Weight (kg)

Document: [REDACTED]

Author: [REDACTED]

Version Number:

2.0

Version Date:

23APR2024

Template No.: CS\_TP\_BS016 Revision 6

Reference: CS\_WI\_BS005

Effective Date: 02Dec2019

Copyright © 2009, 2010, 2012, 2016, 2018, 2019 [REDACTED]. All rights reserved. The contents of this document are confidential and proprietary to [REDACTED] and its subsidiaries. Unauthorized use, disclosure or reproduction is strictly prohibited.

- BMI (kg/m^2)

## 15.5. PHYSICAL, GYNECOLOGICAL, AND BREAST EXAMINATIONS

Clinically significant findings of general physical, gynecological, and breast examinations performed at EOS will be recorded as TEAEs by the Investigator; these findings will be included in the TEAE summaries, as appropriate.

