8.3.1 Physical Examinations

A focused physical examination will be conducted by an Investigator or medically qualified designee (consistent with local requirements) at the Screening (V1) and EOS (V7) Visits as per institutional standard. At a minimum, examination for abnormalities of the heart, lungs, abdomen, and extremities should be performed. Investigators should pay special attention to clinical signs related to previous serious illnesses.

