8.4.1 Time Period and Frequency for Collecting AE and SAE Information

All AEs and SAEs will be collected from the signing of the ICF until EOS/ET (Section [1.3](#)).

From the time of signing ICF through EOS/ET(V7), which is 14 to 19 days after last intake of study drug, all AEs, SAEs, and other reportable safety events must be reported by the Investigator. For the analysis of AEs and SAEs, a distinction will be made between:

- **Pre-Treatment AEs:** Events which occur after the ICF (or assent form, if applicable) is signed and before the first intake of study drug.
- **Treatment-emergent AEs:** Events which occur in temporal association with intake of study drug, until 14 days after the last intake of active study drug.

Additionally, any SAE brought to the attention of an Investigator at any time outside the period specified in the previous paragraph must be reported immediately (within 24 hours of learning about the event) to the Sponsor if the event is considered related to study drug.

Investigators are not obligated to actively seek AEs or SAEs or other reportable safety events in former study participants. However, if the Investigator learns of any SAE, including a death, at any time after a participant has been discharged from the study, and he/she considers the event to be reasonably related to the study drug or study participation, the Investigator must promptly notify the Sponsor.

All initial and follow-up AEs, SAEs, and other reportable safety events will be recorded and reported to the Sponsor or designee within the time frames as indicated in [Table 8](#).

The method of recording, evaluating, and assessing causality of AE and SAE and the procedures for completing and transmitting SAE reports are provided in [Appendix 4](#).

Table 8 Reporting Time Periods and Time Frames for Adverse Events and Other Reportable Safety Events

Type of Event	Reporting Time Period: Signing of ICF to First Intake of Study Drug (Day 1)	Reporting Time Period: First Intake of Study Drug (Day 1) through End of Study (V7)	Time Frame to Report Event and Follow-up Information to Sponsor:
Nonserious Adverse Event (NSAE)	Report if: 
• Due to protocol-specified procedure, or• Causes exclusion	Report all	Per eCRF completion guidelines
Serious Adverse Event (SAE)	Report if: 
• Due to protocol-specified procedure, or• Causes exclusion	Report all	Within 24 hours of learning of event

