### 3.2. CHANGES TO ANALYSIS FROM PROTOCOL

Only safety analyses will be performed for this study. Efficacy and PK analyses will not be performed.

Consequently, the Safety Analysis Set (SAF), Allocated Participants Set (APS), and Multiple Enrollment Set (MES) as described in [Section 5](#) will be used.

The protocol (footnote to Table 11) specifies that laboratory and vital will be analysed up 28 days after last tablet intake; however, the protocol also specifies that the follow-up visit occurs 14 days (+5 days) after the last tablet. Therefore, this is now corrected in the footnote of Table B of the SAP.

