### 15.1. ADVERSE EVENTS

AEs will be coded using MedDRA coding dictionary, Version 26.1 or higher.

Treatment-emergent adverse events (TEAEs) are defined as AEs that started on or after the day of first dose of study treatment (or worsened in severity) and prior to the last date of study treatment + 14 days (inclusive). See Appendix A for handling of partial dates for AEs. In the case where it is not possible to define an AE as treatment emergent or not due to a partial start date, the AE will be classified by the worst case; i.e. treatment emergent. Pre-treatment AEs/SAEs starting before the on-treatment period, including those starting on the day of first dose of study treatment yet prior to the study treatment intake, will be excluded from the TEAE analyses. Pre- and post-treatment AEs will be identified in listings.

---

Document: [REDACTED]

Author: [REDACTED]

Version Number:

2.0

Version Date:

23APR2024

Template No.: CS\_TP\_BS016 Revision 6

Reference: CS\_WI\_BS005

Effective Date: 02Dec2019

Copyright © 2009, 2010, 2012, 2016, 2018, 2019 [REDACTED]. All rights reserved. The contents of this document are confidential and proprietary to [REDACTED] and its subsidiaries. Unauthorized use, disclosure or reproduction is strictly prohibited.

An overview table of number (%) of participants within each of the categories described in the sub-section below will be provided as specified in the templates. The broad AE categories consisting of the percentage of participants with any TEAE, a drug-related TEAE, a serious TEAE, a TEAE that is both drug-related and serious, and a TEAE leading to discontinuation of study treatment will be summarized. Similar Table by BMI group ( $<30 \text{ kg/m}^2$ ,  $\geq 30 \text{ kg/m}^2$ ) will be provided. Listings will include all AEs (including participants who enrolled more than once).

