## 16. APPENDIX A

### 16.1. ALGORITHM FOR TREATMENT EMERGENCE OF ADVERSE EVENTS:

---

Document:

Author:

Version Number:

2.0

Version Date:

23APR2024

Template No.: CS\_TP\_BS016 Revision 6

Reference: CS\_WI\_BS005

Effective Date: 02Dec2019

Copyright © 2009, 2010, 2012, 2016, 2018, 2019 [REDACTED]. All rights reserved. The contents of this document are confidential and proprietary to [REDACTED] and its subsidiaries. Unauthorized use, disclosure or reproduction is strictly prohibited.

AE START DATE	AE STOP DATE	ACTION
Known	Known/Partial/ Missing	
If AE stop date is partial, impute AE stop date as latest possible date (i.e., last day of month if day unknown or 31st December if day and month are unknown).
 
If AE start date < study treatment start date, assign as pre-treatment AE.
 
If AE start date >= study treatment start date and <= study treatment stop date + 14 days, assign as TEAE.
 
If AE start date > study treatment stop date + 14 days, assign as post-treatment AE.

Partial	Known/Partial/ Missing	
If AE stop date is partial, impute AE stop date as latest possible date (i.e., last day of month if day unknown or 31st December if day and month are unknown).
 
Impute AE start date as the study treatment start date, if:
 

the year of the AE start date is equal to the year of the study treatment start date and the AE stop date is later or equal to the study treatment start date or is missing.

the year and month of the AE start date is equal to the year and month of the study treatment start date and the AE stop date is later or equal to the study treatment start date or is missing.

 
Otherwise, Impute AE start date as earliest possible date (i.e. first day of month if day unknown or 1st January if day and month are unknown). Then:
 
If AE start date < study treatment start date, assign as pre-treatment AE.
 
If AE start date >= study treatment start date and <= study treatment stop date + 14 days, assign as TEAE.
 
If AE start date > study treatment stop date + 14 days, assign as post-treatment AE.

Document: [REDACTED]

Author: [REDACTED]

Version Number:

2.0

Version Date:

23APR2024

Template No.: CS\_TP\_BS016 Revision 6

Reference: CS\_WI\_BS005

Effective Date: 02Dec2019

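### SAP 15.5 counts EOS examination findings as TEAEs, but under SAP 15.1 and Appendix 16.1 a finding first dated on days 15 to 19 after the last tablet, five of the six permitted V7 days, is post-treatment

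*SAP*

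**What the plan says.** SAP 15.5 deals with clinically significant findings of the general physical, gynecological and breast examinations. It says that those "performed at EOS will be recorded as TEAEs by the Investigator; these findings will be included in the TEAE summaries, as appropriate". It sets no condition on timing.

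SAP 15.1 defines a TEAE by its start date, with an upper limit of 14 days after the last dose, inclusive. Appendix 16.1 turns this into an algorithm: an AE whose start date is later than "study treatment stop date + 14 days, assign as post-treatment AE". For such events SAP 15.1 says "Pre- and post-treatment AEs will be identified in listings".

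On timing, Protocol 8.4.1 describes the EOS/ET visit (V7) as one "which is 14 to 19 days after last intake of study drug". SAP 3.2 restates this: "the protocol also specifies that the follow-up visit occurs 14 days (+5 days) after the last tablet".

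On content, Protocol 8.3.1 places the physical examination "at the Screening (V1) and EOS (V7) Visits as per institutional standard", and the Schedule of Activities puts the gynecological and breast examinations at the same two visits. SAP Table A lists as a primary safety endpoint "Abnormalities in clinical laboratory assessments, vital signs, and physical examination".

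**The concern.** SAP 15.5 and Appendix 16.1 classify the same event by different rules. The first uses where the finding was made (the EOS examination), the second uses when the event started. They disagree for a finding first dated on days 15 to 19, and these are ordinary, on-schedule visit days.

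The programmer must choose one rule, and the choice decides whether a new breast, gynecological or physical finding is counted in a summary table or appears only in a listing. The stake is more than editorial for three reasons:

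- Safety is the only objective still analyzed (SAP 2 and 3.2), and Table A names examination abnormalities in a primary endpoint.
- The SAP text describes no summary of examination findings other than the TEAE tables.
- Protocol 9.4.3 counted delayed events or diagnoses as on-treatment if the Investigator judged them drug-related. The SAP has no such rule and does not list its removal in 3.2. Protocol 9.4 says that the SAP prevails where the two differ.

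**Working it through.** **Step 1. The visit window.** Inputs: V7 target 14 days after last intake, window +5 (Schedule of Activities; SAP 3.2). Permitted days are 14 + 0 to 14 + 5, that is 14, 15, 16, 17, 18 and 19: six days. This reproduces the 14 to 19 days stated in Protocol 8.4.1.

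**Step 2. The TEAE limit.** Input: start date no later than last tablet + 14 is a TEAE, later is post-treatment (SAP 15.1; Appendix 16.1). Day 14 is inside. Days 15 to 19 are outside: 5 of 6 days, and 5/6 = 83%.

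**Step 3. Check on treatment days for a 13-cycle completer.**

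- Last tablet: 13 × 28 = Day 364.
- TEAE limit: 364 + 14 = Day 378.
- Permitted V7: Days 378 to 383.
- SAP Table B centers V7 on Day 379, and 379 − 364 = 15. The SAP's own nominal V7 day is therefore one day past its TEAE limit.

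**Step 4. From visit days to findings.** Appendix 16.1 uses the AE start date, not the examination date. Let *s* be the share of findings made at visits held on day 14, and *q* the share of findings at later visits whose recorded onset is after day 14. For visits on schedule, the share leaving the TEAE tables is (1 − *s*) × *q*. The documents give neither quantity, so the values below are assumptions.

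| Assumption | *s* | *q* | Share leaving |
|---|---|---|---|
| Findings spread evenly over the six days, onset = visit date | 1/6 | 1 | 83% |
| Even spread, half of onsets after day 14 | 1/6 | 0.5 | 42% |
| Half on day 14, onset = visit date | 0.5 | 1 | 50% |
| 80% on day 14, onset = visit date | 0.8 | 1 | 20% |
| Every onset dated by day 14 | any | 0 | 0% |

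The 83% is the even-spread value, not a mathematical ceiling. With no visit on day 14 and every onset dated at the visit, the formula gives (1 − 0) × 1 = 100%.

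**Step 5. The protocol's own period.** Protocol 9.4.3 counts 14 days from the last active tablet. For a completer that tablet falls on 12 × 28 + 24 = Day 360, so the period ends on Day 374 and all six V7 days (378 to 383) lie outside, apart from delayed events judged related. The SAP counts from the last tablet of any kind. Its window is four days longer, but the exception for delayed related events is gone.

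**The case against.** The best defense is that 15.5 was never meant as a second classification rule. Its sentence ends with the qualifier *as appropriate*, which can be read as: the Investigator records the finding, and it enters the TEAE tables if it meets 15.1 and 16.1. Protocol 9.4.3.4 supports this, because it says only that such findings are recorded as AEs. The protocol synopsis also limits the primary safety analysis of examination abnormalities to the on-treatment period, so keeping out an event with a known later onset follows the endpoint. No data are lost, since all AEs are listed.

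Much of this stands. It is the more natural reading, and it is a good reason not to alter 16.1. It does not remove the problem. The qualifier does not say which rule governs. If 16.1 governs, findings dated on days 15 to 19 at an on-schedule visit leave every summary that the SAP text describes for this part of the endpoint.

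One limit should be stated. SAP 8 says that the templates supplied with the SAP define the outputs. They are not in the text available here, so an examination table could exist there.

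A reader might go further and infer that most V7 findings drop out, or that the examination part of the endpoint is nearly empty by construction. The documents do not support that:

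- They give no distribution of V7 dates, and day 14, the target day, is inside the window.
- A finding with onset dated on or before day 14 stays a TEAE whenever it was examined.
- Appendix 16.1 often resolves partial or missing start dates toward TEAE. For example, an AE with neither a start nor a stop date is taken as a TEAE.
- V7 is the only scheduled post-baseline examination, but Protocol 8.3.2 also allows gynecological and breast examinations whenever clinically indicated.

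**Conclusion.** The inconsistency is real and should be resolved. A clinically significant finding first dated on days 15 to 19 is a TEAE under SAP 15.5 and post-treatment under SAP 15.1 and Appendix 16.1. Five of the six permitted V7 days are exposed to this.

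The number of findings affected is unknown. The scenarios tried run from 0% to 83%, and the top of that range needs both an even spread over the window and an onset dated on the visit day. The conclusion rests on visits held within the stated window and on the SAP text as available, without its output templates. It concerns how findings are summarized, not whether they are collected or listed.

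**What to change.** 1. In SAP 15.5, state that EOS examination findings are recorded as AEs and that their TEAE status follows 15.1 and Appendix 16.1. Leave 16.1 unchanged. A special branch there for findings detected at V7 would put events that began after the on-treatment period into the TEAE tables, against the protocol synopsis and SAP 15.1.

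2. Add one descriptive table of clinically significant V7/ET physical, gynecological and breast findings not present at V1, regardless of TEAE status. Give n and the percentage of SAF participants attending V7/ET, with a flag for onset more than 14 days after the last tablet. Attendance is a workable denominator because Protocol 8.3.2 has only abnormal gynecological and breast findings recorded, so a count of women examined may not be available.

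The cost is one sentence, one flag and one small table. The downside is that the table will include a few findings that began just after the on-treatment period, and the flag lets the reader set them apart.
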